Statistical methods	
Analysis of primary endpoint: For each of 100 imputed data sets, the difference in response rates between treatment groups will be analysed using the Mantel-Haenszel risk difference stratified by prior CSA use (yes/no) and baseline disease severity (IGA 3 or 4). The estimates and standard errors from the 100 analyses will be pooled to one estimated treatment difference and associated standard error using Rubin's rule to draw inference. From these pooled estimates, the 95% CI for the treatment difference will be calculated. Subjects who prior to the relevant visit receive rescue treatment or permanently discontinue IMP, without prior subject-onset of the COVID-19 pandemic, will be imputed as non-responders. Any missing or collected data from subjects who have subject-onset of the COVID-19 pandemic as their first prior

	
intercurrent event will be imputed assuming missing at random (MAR). Data missing prior to any intercurrent event will be handled as non-response, unless data is missing due to the COVID-19 pandemic, in which case it will be imputed assuming MAR.
 
Analysis of secondary efficacy endpoints: Secondary binary endpoints at Week 16 and Week 26 will be analysed as described for the primary endpoint.
 
Secondary continuous endpoints will be analysed using a model for repeated measurements approach with prior CSA use (yes/no), country (Germany: yes/no), baseline disease severity (IGA 3 or 4) and treatment-by-visit interaction as factors and baseline score-by-visit interaction as a continuous covariate.
 
Analysis of secondary safety endpoints: Number of adverse events will be summarised by treatment, system organ class, and preferred term. The frequency of anti-drug antibodies will be summarised by treatment.

Signatory investigator
	
PPD [REDACTED], [name]. med PPD [REDACTED], Germany

Sponsor
	
LEO Pharma A/S, [name]

2 Trial identification

[figure not shown]
EudraCT number: 2018-000747-76

IND number: 123797

The clinical trial protocol will be registered in local registries if required by local legislation.

3 Schematic of trial design

Panel 1: Trial design

Abbreviations: AD: atopic dermatitis; No: number; TCI: topical calcineurin inhibitors; TCS: topical corticosteroids; Q2W: every other week; w: week.

4 Schedule of trial procedures

Panel 2: Schedule of trial procedures: screening and treatment period

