14.3.8.1 Primary estimand: ‘COVID-19 modified composite’

The primary estimand for the primary endpoint will be:

- Treatment difference in response rates of EASI75 after 16 weeks achieved without rescue treatment and treatment discontinuation, as if the COVID-19 pandemic did not happen

The primary estimand assesses the expected difference in response rates (defined as response obtained without initiation of any rescue treatment and/or permanent discontinuation of IMP) after 16 weeks, resulting from initiation of a treatment regimen with tralokinumab+TCS compared to a treatment regimen with placebo+TCS.

Primary analysis for the primary estimand

Subjects who prior to the Week 16 visit have received rescue treatment or permanently discontinued IMP, without subject-onset of the COVID-19 pandemic, will be considered non-responders at all visits after the relevant event occurs ([Panel 13](#)).

The non-responder imputation reflects an assumption that such initiation of rescue treatment and permanent discontinuation of IMP indicates failure of the randomised treatment to achieve response. Furthermore, this reflects that a (possible) observed positive response after initiation of rescue treatment or permanent discontinuation of IMP is not attributable to the randomised treatment.

Any missing or collected data from subjects who have subject-onset of the COVID-19 pandemic as their first prior intercurrent event will not be used, but instead imputed assuming missing at random (MAR) following the start of subject-onset of the COVID-19 pandemic.

Data missing prior to any intercurrent event will be handled as non-response, unless data is missing due to the COVID-19 pandemic, in which case it will be imputed assuming MAR.

The procedure for imputing values according to the rules described will be implemented in a 2-step procedure, where all missing or ignored data (irrespective of reason) initially will be imputed using MAR based on available data from all subjects. The non-responder imputation of data not affected by the COVID-19 pandemic will be handled subsequently.

The initial MAR imputation will be implemented using the same multiple stepwise imputation method as specified in Section 14.3.8.4 for the primary analysis of the hypothetical binary estimand. The multiple imputation (MI) procedure sequentially builds 100 complete data sets by stepwise use of an ANCOVA model from Week 2 to Week 16 assuming MAR within treatment groups.

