14.3.8.4 Quaternary estimand: ‘hypothetical’

The quaternary estimand for the primary endpoint will be:

- Treatment difference in response rates of EASI75 after 16 weeks if all subjects adhered to the treatment regimen in the sense that they did not discontinue IMP permanently, no rescue treatment was made available, and as if the COVID-19 pandemic did not happen before Week 16.

The quaternary estimand assesses the expected difference in response rates achieved when adhering to the treatment regimen tralokinumab+TCS with no rescue treatment or subject-onset of the COVID-19 pandemic as compared to a treatment regimen with placebo+TCS with no rescue treatment or subject-onset of the COVID-19 pandemic.

Primary analysis of the quaternary estimand

Data collected after permanent discontinuation of IMP, after initiation of rescue treatment, or after subject-onset of the COVID-19 pandemic will not be applied in the analysis ([Panel 13](#)).

EASI75 responder imputation

Imputation of missing binary EASI75 data at Week 16 will be done using multiple imputations of the underlying 72-point EASI values within the 2 groups defined according to randomised treatment group assuming that data is MAR within each group.

1. Intermittent missing values will be imputed in each group using a Markov Chain Monte Carlo method to obtain a monotone missing data pattern and 100 copies of the dataset will be generated (seed=12456746).
2. For each of the 100 copies of the dataset, an analysis of covariance (ANCOVA) model is fitted to the EASI value at Week 2. The model will include effects of baseline EASI as a covariate, and prior CSA use (yes/no), and baseline disease severity (IGA 3 or 4) as factors. The estimated parameters, and their variances, will be used to impute missing EASI values at Week 2 (seed=12576546).
3. For each of the 100 copies of the dataset, missing EASI values at Week 4 will be imputed in the same way as for Week 2. The imputations will be based on the same ANCOVA model with effects of baseline EASI as a covariate, and prior CSA use, country, and baseline disease severity as factors together with the EASI value at Week 2 as covariate. The estimated parameters, and their variances, will be used to impute missing values at Week 4.

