For each of the 100 imputed dataset, the change from baseline in SCORAD at Week 16/ Week 26 will be analysed using an ANCOVA model with effects of treatment, prior CSA use, country, baseline disease severity, and baseline SCORAD value as factors. The estimated difference at Week 16/ Week 26 will be derived together with the associated standard error. The estimates and standard errors from the 100 analyses are pooled to one estimate and associated standard error using Rubin's rule to draw inference. From these pooled estimates, the 95% CI for the treatment difference will be calculated.

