For discontinued subjects, it is expected that the number of subjects with retrieved data at Week 16/ Week 26 will be too small to facilitate the same imputation model as mentioned just above. Consequently, an imputation model with prior CSA use (yes/no), country (Germany: yes/no), and baseline disease severity (IGA 3 or 4) as factors and baseline SCORAD/DLQI as a covariate will be applied for discontinued subjects. Some factors may have to be omitted, depending on the observed data, e.g. all subjects have the same baseline disease severity. In that case, the preferred order of elimination of the effects from the imputation model will be: country, prior CSA use, baseline disease severity, and baseline SCORAD/DLQI (seed=12576546).

Each of the 100 imputed datasets will be analysed as described in the sensitivity analyses for the primary estimand for the continuous secondary endpoints (see [Section 14.3.9.1](#)).

Sensitivity analyses for the secondary estimand (continuous secondary endpoints)

Rather than assuming that observations are MAR, it is assumed that missing data from subjects in the tralokinumab+TCS group who have/have not discontinued treatment prior to Week 16/ Week 26 will resemble data from subjects from the placebo+TCS group who have/have not discontinued treatment prior to Week 16/ Week 26.

Imputation of missing data at Week 16/ Week 26 will be done using a pattern mixture model where missing data in the tralokinumab+TCS group as well as the placebo+TCS group will be imputed from the placebo+TCS group (copy-reference approach). With this exemption, the MI procedure and analysis will be conducted in the same way as described for the primary analysis of the secondary estimand for the continuous secondary endpoints (Section 14.3.9.2).

**14.3.9.3 Tertiary estimand for the continuous secondary endpoints:
'COVID-19 modified composite'**

The primary estimand for the continuous tertiary endpoint will be:

- Treatment difference in change from baseline to Week 16/Week 26 in SCORAD and DLQI scores, respectively, without rescue treatment and treatment discontinuation, as if the COVID-19 pandemic did not happen

The continuous tertiary estimand assesses the expected treatment difference (obtained without initiation of any rescue treatment and/or permanent discontinuation of IMP) after 16/ 26 weeks, resulting from initiation of a treatment regimen with tralokinumab+TCS compared to a treatment regimen with placebo+TCS.

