Primary analysis for the tertiary estimand (continuous secondary endpoints)

Data retrieved at Week 16/ Week 26, depending on the endpoint, for subjects who have received rescue treatment or permanently discontinued IMP prior to the visit, without subject-onset of the COVID-19 pandemic, will be considered non-responders by using worst observation carried forward (including the baseline value) (Panel 13).

Any missing or collected data from subject who have subject-onset of the COVID-19 pandemic as their first prior intercurrent event will not be used, but instead be imputed assuming MAR following the start of subject-onset of the COVID-19 pandemic.

Any data missing at the relevant visit from subjects without prior rescue treatment, permanent discontinuation of IMP, or subject-onset of the COVID-19 pandemic will be imputed assuming MAR.

The procedure for imputing values according to the rules described above will follow the same imputation procedure described in the primary analysis of the binary primary estimand. However, any data missing at the relevant visit from subjects without a prior intercurrent event will not be imputed as a ‘non-responder’ after the imputation step, but will be imputed assuming MAR.

For each of the resulting 100 imputed datasets, this primary analysis will be analysed using an ANCOVA model with effects of treatment, prior CSA use (yes/no), country (Germany: yes/no) and baseline disease severity (IGA 3 or 4) as factors. The estimates and standard errors from the 100 analyses are pooled to one estimate and associated standard error using Rubin’s rule to draw inference. From these pooled estimates, the 95% CI for the treatment difference will be calculated.

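### The ANCOVA for SCORAD and DLQI change under the COVID-19 modified composite estimand leaves out the baseline score, which every other written-out model for these changes includes

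*Protocol*

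**What the plan says.** Protocol 14.3.9.3 defines the estimand as "Treatment difference in change from baseline to Week 16/Week 26 in SCORAD and DLQI scores, respectively, without rescue treatment and treatment discontinuation", as if the pandemic had not happened. Subjects with rescue treatment or IMP discontinuation as first event get the worst observation carried forward (WOCF), baseline included. Values after subject-onset of the pandemic, and values missing without a prior event, are imputed under MAR. Each of the 100 datasets is then analysed with an "ANCOVA model with effects of treatment, prior CSA use (yes/no), country (Germany: yes/no) and baseline disease severity (IGA 3 or 4) as factors", and results are pooled by Rubin's rule.

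The other places that bear on the model are:

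- **Synopsis and Protocol 14.3.9.1, repeated measurements model:** includes "baseline score-by-visit interaction as a continuous covariate".
- **Protocol 14.3.9.1, sensitivity ANCOVA on imputed data:** the listed effects end with "baseline disease severity, and baseline SCORAD value".
- **Protocol 14.3.9.2, treatment policy:** uses that same ANCOVA by cross-reference.
- **Protocol 14.3.9.4, subgroup model for the primary estimand:** includes baseline SCORAD by visit.
- **Imputation for this estimand:** it "will follow the same imputation procedure described in the primary analysis of the binary primary estimand". Protocol 14.3.8.1 in turn states: "The initial MAR imputation will be implemented using the same multiple stepwise imputation method as specified in Section 14.3.8.4". There, "The model will include effects of baseline EASI as a covariate".
- **SAP 6.6.3.2, tertiary estimand:** adds country to the imputation variables and leaves the analysis model unchanged.

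**The concern.** A change score with no baseline term fixes the slope of follow-up on baseline at 1. If the true slope differs, two things follow. The residual variance is larger than it need be, and a chance baseline difference between arms is over- or under-corrected, except for the part that the two-level baseline IGA factor absorbs.

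There is also a question of reading the results. The three continuous estimands are meant to differ in how they handle intercurrent events. If this one also has a different covariate set, a discrepancy between its result and the others mixes an estimand effect with a modelling effect.

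Bias and error rate are not at stake. Protocol 14.3.6 bases testing on the primary estimand, which for SCORAD and DLQI is the hypothetical one and already adjusts for baseline score.

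**Working it through.** **1. Is there a counter-example?** The models for TCS amount and for days without topical treatment (Protocol 14.3.10, SAP 6.6.5) also lack a baseline score, but those outcomes are not changes from baseline. Among models for SCORAD or DLQI change, 14.3.9.3 is the only one without it. No reason is given.

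**2. Inputs.** The documents give 250 subjects, 1:1 allocation and two-sided 5% tests. Their power statements concern binary endpoints and reproduce: EASI75 at 40% v 15% gives 99.5% (stated 99%), and itch at 30% v 15% gives 81.4%, about 81% jointly (stated at least 80%). Nothing is given on SDs, correlations, WOCF share or imputed share for SCORAD or DLQI. Those values are assumed below.

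**3. Cost.** Residual degrees of freedom are 250 − 5 = 245 as written and 250 − 6 = 244 with a linear baseline term. The t quantile is 1.9697 in both cases. If the true slope is exactly 1, the CI widens by a factor of about √(1 + 1/243) = 1.002.

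**4. Gain in large samples, before WOCF and IGA.** Let s0 and s1 be the baseline and follow-up SDs and r their correlation.

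- Change score variance: s0² + s1² − 2·r·s0·s1
- Baseline-adjusted variance: s1²·(1 − r²)
- Difference: (s0 − r·s1)², which is never negative

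At r = 0.2:

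- DLQI with SDs 7 and 6.5: 73.05 v 40.56, so the SE ratio is √1.801 = 1.34.
- SCORAD with SDs 12 and 18: 381.6 v 311.04, so the SE ratio is √1.227 = 1.11.

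For SCORAD the gain almost disappears near r = 0.6, where the slope is 0.6 × 18/12 = 0.9.

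**5. Gain with WOCF, imputation and IGA included.** WOCF values track baseline and IGA is already in the model, so both shrink the gain. A simulation of the pooled SE used:

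- 250 subjects 1:1, baseline plus four follow-up visits, adjacent follow-up correlation 0.75;
- stepwise MAR imputation within arm from baseline score, two preceding visits, CSA use, country and IGA, followed by WOCF and Rubin's rule;
- r from 0.2 to 0.8, 15–40% WOCF and 10–25% imputed, with WOCF either unrelated to outcome or likelier with poor outcome;
- assumed means for DLQI of 17 at baseline, then 9 (placebo) and 6 (tralokinumab), and for SCORAD of 70, then 42 and 34.

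| Setting | DLQI (7 / 6.5) | SCORAD (12 / 18) |
|---|---|---|
| SE ratio without/with baseline, all settings | 0.998–1.204 | 0.999–1.055 |
| Middle case (r = 0.4, 25% WOCF, 10% imputed): 95% CI half-width without v with | 2.02 v 1.82–1.92 (5–11%) | 5.38 v 5.32 at most (0.1–1.2%) |
| Largest case (r = 0.2, 15% WOCF, 10% imputed): half-width without v with | 2.23 v 1.86 | 5.60 v 5.32 |

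There is no gain for SCORAD at r = 0.6, or for DLQI at r = 0.8, when WOCF is linked to poor outcome at 25–40%.

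A separate simulation with equal SDs, a 20% WOCF share and IGA in the model gave SE ratios with/without of 0.92, 0.95 and 0.98 at r = 0.3, 0.5 and 0.7. Mean treatment estimates were the same with and without the term.

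**6. Chance imbalance.** A one-SE baseline difference is SD × √(4/250): 7 × 0.1265 = 0.89 DLQI points and 12 × 0.1265 = 1.52 SCORAD points. Simulated outcome-on-baseline slopes ran from 0.28 to 1.05 (DLQI) and from 0.38 to 1.53 (SCORAD). The largest mis-correction is then 0.72 × 0.89 ≈ 0.6 DLQI points and 0.62 × 1.52 ≈ 0.9 SCORAD points.

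**The case against.** The strongest reply is that nothing turns on this. The analysis is valid, supportive and untested, and the analyses that carry the inference already adjust for baseline. That is correct, and it is why the point is minor. It is not a reason to leave out a free improvement.

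A second reply is that this is a drafting slip. A model called ANCOVA would normally have a continuous covariate, and the nearby text is loose: the sensitivity ANCOVA in 14.3.9.1 lists the baseline score among the factors. That may be so, and the programmed model may include the term. The text as it stands does not, and the SAP revisited this estimand without restoring it.

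The third reply concerns the numbers, and part of it stands.

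- **SD ratio.** It matters as much as r, and the ranges above hold one SD pair per endpoint fixed. At r = 0.4 and 25% WOCF, DLQI SDs of 6 and 7.5 gave a gain of 2–4%, DLQI SDs of 7 and 5 gave 11–17%, and SCORAD SDs of 14 and 14 gave 3–6%. Across other SD pairs the DLQI gain ran from about 0 to 30%.
- **IGA correlation.** The main grid took 0.3 between IGA and baseline score. At 0.6 the DLQI gain fell, for example from 10.8% to 8.6%.
- **Simplifications.** The simulation used four follow-up visits and 20–30 imputations rather than the planned visit sequence and 100. It did not model the step for intermittent gaps or truncation to scale.

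These points change the size of the gain. None makes adding the term harmful beyond the 0.2% in step 3.

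**Conclusion.** The omission is real and unexplained, and it is out of line with every other written-out model for SCORAD and DLQI change. It is a minor matter of precision and consistency across estimands, and no confirmatory conclusion depends on it.

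Under the assumed SDs the standard error is 0–20% larger than necessary for DLQI and 0–6% larger for SCORAD. For SCORAD the middle case is negligible. These ranges depend on the SD pairs, correlations, and WOCF and imputed shares named above, none of which the documents supply. What does not depend on them is that the large-sample variance with the baseline term is never larger.

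**What to change.** Before the randomisation code is broken, state in SAP 6.6.3.2, under the primary analysis of the tertiary estimand, that the ANCOVA of Protocol 14.3.9.3 also includes baseline SCORAD (or baseline DLQI) as a continuous covariate. The word continuous matters: entered as a factor, as the 14.3.9.1 wording would literally have it, the score would use many degrees of freedom instead of one. Protocol 14.3.16 allows such a change to be described and justified in the SAP.

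The cost is one phrase and one degree of freedom. No subject is lost, because SAP 6.8.1 already excludes subjects without a baseline value from change endpoints. If the code has already been broken, report the adjusted model beside the planned one and label it as added afterwards.

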14.3.9.4 Subgroup analysis of continuous endpoints

Subgroup analyses will be performed for the SCORAD and DLQI endpoints at Week 16 and Week 26 for the following groups: sex, prior CSA use, baseline disease severity (IGA 3 or 4), country, age (≤ 65 years, > 65 years) for the primary analysis of primary and secondary estimands. For the primary estimand the following repeated measurements model with an unstructured covariance matrix and Kenward-Roger approximation of degrees of freedom will be applied (presented for subgroup sex).

Change from baseline in SCORAD

= sex \times treatment \times visit + baseline SCORAD \times visit + CSA use + country + baseline IGA.

The interaction between sex and treatment effect will be tested at Week 16 and Week 26.

14.3.10 Analysis of other endpoints

All binary endpoints listed under ‘Other endpoints’ (Panel 4) will be analysed as for the primary analysis of the primary and secondary estimands for the primary endpoint and presented for the FAS at Week 16 and Week 26.

All continuous endpoints listed under ‘Other endpoints’ (Panel 4) will be analysed as for the primary analysis of the primary and secondary estimands for the continuous secondary endpoints. For the Eczema-related Sleep NRS score, the mean over the last 7 days prior to randomisation will be used as the baseline value. For the Worst Daily Pruritus NRS and Eczema-related Sleep NRS scores, it is expected that subjects will return their eDiaries upon permanent discontinuation of IMP, and no data is available after that point. Thus, analysis

using the primary analysis of the secondary continuous estimand will not be possible in the ‘Other endpoints’ with Worst Daily Pruritus NRS or Eczema-related Sleep NRS scores.

To evaluate the efficacy related to health care resource utilisation, the amount of TCS used (assessed as the amount of TCS used between visits) will be determined over 2-week periods, and the number of days without topical treatment use (collected as Patient Days of Topical Treatment Use in the eDiary) will be determined over 1-week periods. The amount of TCS used and the number of days without topical treatment use will each be analysed using a repeated measurements model with an unstructured covariance matrix and the mean modelled as follows:

$$Y = \text{treatment} \times [\text{visit/week}] + \text{prior CSA use} + \text{country} + \text{baseline IGA}$$

where ‘Y’ is either the amount of TCS used or the number of days without topical treatment use. Data obtained after permanent discontinuation of IMP, after initiation of rescue treatment, or after subject-onset of the COVID-19 pandemic will be excluded from the analyses.

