9.2.2 Administration of AxMP

The IRT will assign the required AxMP (TCS) kit numbers for each subject at each dispensing visit. The TCS will be provided as mometasone furoate, 0.1% cream in kit sizes of 180–225 g Q2W. If needed, additional TCS kit(s) may be dispensed to the subject at a scheduled or unscheduled visit at the investigator's discretion. The amount of additional TCS dispensed must be recorded in the eCRF.

Subjects will be instructed to apply a thin film of the dispensed TCS (Europe: Class 3 [potent]) once daily to active lesions, as needed. The TCS should be discontinued when control is achieved; discontinuation should preferably be gradual and the maximum duration of treatment should not exceed 3 weeks. The safety and appropriateness of continued or repeated courses of TCS therapy will be monitored and supervised by site staff.

From randomisation (Week 0) and until last administration (at Week 24), the TCS will be dispensed and the subject must return used and unused TCS tubes at each subsequent trial visit, to assess the amount of medication used. The subjects must be instructed by the site staff on the importance of returning all used and unused TCS tubes. The site staff will return used and unused TCS tubes to the contract manufacturing organisation (CMO). The TCS tubes will be weighed at the CMO before shipment to the trial sites and again upon return.

An additional, lower potency TCS or TCI may be used at the investigator's discretion on areas of the body where use of the supplied TCS is not advisable such as areas of thin skin (face, skin fold areas, genital areas, etc.) or on areas where continued treatment is considered unsafe. The lower potency TCS and TCI will not be provided by LEO and will not be weighed, but must be registered in the eCRF as concomitant medications (see Section 9.6).

Further details on TCS dispensing are provided in the trial product handling manual. TCS administration must be carried out according to these instructions.

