9.3 Treatment assignment

Randomisation

Subjects who have been found to comply with all the inclusion criteria and not to violate any of the exclusion criteria will be randomised centrally at baseline (Day 0) to receive treatment with either tralokinumab 300 mg+TCS or placebo+TCS, stratified by prior CSA use (yes/no), country (Germany: yes/no), and baseline disease severity (IGA 3 or 4).

The IRT will be used to control randomisation and stratification factors, along with trial product supply chain and expiry tracking.

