11.2.4 Body surface area involvement

The total body surface area (BSA) affected by AD will be assessed by the investigator for each section of the body as component A of SCORAD (see Section 11.3.3) and will be reported as a percentage of all major body sections combined. The following body regions will be assessed (brackets show the highest possible score for each region): head and neck (9%), anterior trunk (18%), back (18%), upper limbs (18%), lower limbs (36%), and genitals (1%). The total BSA score will be assessed according to the schedule of trial procedures (Section 4).

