Appendix 6: Eligibility criteria

A short form (maximum 200 characters) version of each of the eligibility criteria for the trial is provided below, to be used when data are submitted to the FDA.

No.	Inclusion criteria
1	Signed and dated informed consent has been obtained prior to any protocol-related procedures
2	Age 18 years and above
3	Diagnosis of AD as defined by Hanifin and Rajka 1980 criteria for AD
4	History of AD for 1 year or more
5	Subjects with a history within 1 year prior to screening of inadequate response to treatment with topical medications or subjects for whom topical treatments are otherwise medically inadvisable
6	AD involvement of 10% (or more) body surface area at screening and baseline (visit 3) according to component A of SCORAD
7	EASI score of 20 (or more) at screening and baseline
8	An IGA score of 3 or more at screening and at baseline
9	A Worst Daily Pruritus numeric rating scale average score of 4 or more during the week prior to baseline
10	Subjects must have applied a stable dose of emollient twice daily (or more, as needed) for at least 14 days before randomisation
11	Women of child-bearing potential must use a highly effective form of birth control, confirmed by the investigator, throughout the trial and at least for 16 weeks after last administration of IMP
12	Documented history of either no previous CSA exposure and not currently a candidate for CSA treatment OR previous exposure to CSA in which case CSA treatment should not be continued or restarted

No.	Exclusion criteria
1	Subjects for whom TCSs are medically inadvisable in the opinion of the investigator
2	Concurrent enrolment in another interventional clinical trial
3	Previous randomisation in a tralokinumab trial
4	Active dermatologic conditions that may confound the diagnosis of AD or would interfere with assessment of treatment, such as scabies, cutaneous lymphoma, or psoriasis
5	Known active allergic or irritant contact dermatitis that is likely to interfere with the assessment of severity of AD
6	Use of tanning beds or phototherapy (NBUVB, UVB, UVA1, PUVA), within 6 weeks prior to randomisation

7	Treatment with immunomodulatory medications or bleach baths within 4 weeks prior to randomisation
8	Treatment with PDE-4 inhibitor within 2 weeks prior to randomisation
9	Receipt of live attenuated vaccines within 30 days prior to the date of randomisation and during the trial including the safety follow-up period

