#### Amount of TCS used

The amount of TCS used will be calculated as specified in section 6.6.8 and analysed in two ways, reflecting the two consumption assumptions. The primary analysis will be using the most conservative assumption that all missing tubes were fully used. The second assumption will be used as a sensitivity analysis, reflecting the primary analysis’s extreme opposite, that all non-returned tubes were not used. The method used for analysis will be the one specified in the protocol. Additionally, descriptive histograms of both consumption assumptions will be produced.

In an extra sensitivity analysis, the amount of TCS used will be log transformed. This transformation has in a similar trial proven to fit data better. TCS amount will be log transformed by adding 1 (due to potential zero values) and then taking the logarithm. The analysis will use the same repeated measures model with the mean modelled as follows:

$$\log[\text{TCS amount used} + 1] (g) = \text{Treatment} * \text{visit} + \text{prior CSA use} + \text{country} + \text{Baseline IGA}$$

The analysis results will be presented by back-transforming using the exponential function, thus producing estimated geometric means and estimated ratio of means, which will be presented with nominal p-values and 95% confidence intervals (CI). This sensitivity analysis will be done for both consumption assumptions.

Additionally, descriptive histograms of both consumption assumptions will be produced for the amount of TCS.

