#### Number of days without topical treatment use

The number of days without topical treatment use will be analysed as specified in the protocol. Number of days without topical treatment use will be calculated using the same rules as for the Worst Daily Pruritus NRS (weekly average).

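### The model for amount of TCS used has no continuous measure of baseline eczema extent, although one is collected on every subject, so some precision may be lost

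*Protocol*

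**What the plan says.** Protocol 14.3.10 covers both health care resource endpoints in one sentence: "The amount of TCS used and the number of days without topical treatment use will each be analysed using a repeated measurements model". The covariance matrix is unstructured, and the mean is treatment x [visit/week] + prior CSA use + country + baseline IGA. Grams of TCS are taken over 2-week periods and days without topical treatment over 1-week periods.

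SAP 6.6.5 leaves this unchanged. For grams: "The method used for analysis will be the one specified in the protocol". For the added log(amount + 1) sensitivity analysis: "The analysis will use the same repeated measures model with the mean modelled as follows", and the terms listed are the same. For days: "The number of days without topical treatment use will be analysed as specified in the protocol".

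On how the cream is used, Protocol 9.2.2 has subjects apply it "once daily to active lesions, as needed". On what is measured, Protocol 11.2.4 says "The total body surface area (BSA) affected by AD will be assessed by the investigator for each section of the body", and Panel 2 schedules this at screening and baseline. Entry requires "AD involvement of 10% (or more) body surface area at screening and baseline (visit 3) according to component A of SCORAD", and also EASI of at least 20 and IGA of at least 3 at baseline (Protocol 8.2).

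**The concern.** If cream goes on active lesions, a subject with more lesional skin should, other things equal, use more grams. The only disease measure in the model is a two-level IGA, which does not quantify area. Variation in use that baseline extent could explain stays in the residual, and the confidence interval for the difference in grams is wider than it need be. A chance imbalance in extent between the arms is also left unadjusted.

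The repeated-measures model for SCORAD and DLQI (Protocol 14.3.9.1) does carry a continuous baseline score by visit. TCS amount is recorded only from Week 0, so it has no baseline value of its own, and no prognostic substitute was put in that place. The documents give no reason for leaving one out.

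What is at stake is the precision of the steroid-use comparison, which the trial uses to describe health care resource utilisation.

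**Working it through.** **The plan's own figures.** The documents state no SD, effect size, power or correlation for TCS amount, so there is nothing to reproduce on this endpoint. The 99% power in Protocol 14.1 (40% vs 15%, 125 per arm, two-sided 5%) reproduces at 99.5%, but it does not depend on this model.

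**Inputs.**
- N = 250, randomised 1:1 (Protocol synopsis).
- Current between-subject parameters at one period: intercept, treatment, prior CSA use, country and IGA, so 5. One covariate makes 6.
- r: the partial correlation between baseline BSA and grams used, given IGA, prior CSA use and country. It is not in the documents and is assumed over a range.

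**Formulas** (single-period approximation, no dropout).
- SE ratio, adjusted to current = sqrt(1 - r^2) x sqrt((250 - 5)/(250 - 6)). The second factor, sqrt(245/244) = 1.002, is the price of one degree of freedom.
- Equivalent N = 250/(1 - r^2).
- The last column assumes, for illustration, that power without the covariate is 80%.

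| Assumed partial r | Change in SE | Equivalent N | Power if 80% before |
|---|---|---|---|
| 0 | +0.2% | 250 | 79.8% |
| 0.1 | -0.3% | 253 | 80.2% |
| 0.2 | -1.8% | 260 | 81.4% |
| 0.3 | -4.4% | 275 | 83.4% |
| 0.4 | -8.2% | 298 | 86.2% |
| 0.5 | -13.2% | 333 | 89.8% |

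Example, r = 0.3: sqrt(0.91) x 1.002 = 0.954 x 1.002 = 0.956, so the SE falls by 4.4%. Equivalent N = 250/0.91 = 275.

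**How much IGA already absorbs.** Suppose that extent drives use and that IGA is a median split of a latent severity correlated 0.4 to 0.8 with extent (assumptions). A raw correlation of 0.3 between extent and grams then leaves a partial r of 0.24 to 0.29, an SE gain of 2.8 to 4.2%. A raw 0.5 leaves 0.41 to 0.48, a gain of 8.6 to 12.3%. These gains omit the 0.2% degree-of-freedom cost. IGA takes up part of the signal, but under these assumptions not most of it.

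**Parameters.** There are 26/2 = 13 two-week periods. A main effect costs one slope; a by-visit interaction needs 13. With a main effect, the gain in any one period is smaller than the table shows where that period's slope differs from the shared one.

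**The case against.** The strongest objection is that nobody has shown baseline extent to be a good predictor. A reader might infer from the lesion-directed application that extent largely drives cream use. The documents do not support that:
- TCS is stopped once control is achieved (Protocol 9.2.2), so later use follows current lesions rather than baseline ones.
- Lower-potency TCS or TCI on sensitive areas is not weighed (same section).
- Unreturned tubes count as fully used in the primary analysis (SAP 6.6.5 and 6.6.8), which adds variation that need not relate to extent.
- Entry criteria narrow the spread. With 10 to 29% involvement in every region the area score is 2, and the largest possible EASI is 12 x 2 x (0.1 + 0.3 + 0.2 + 0.4) = 24, against an entry minimum of 20.

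All of this stands, and it is why the table starts at r = 0.

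A reader might also infer that the model is blind to extent. It is not quite: the IGA descriptors in Panel 7 separate grades 3 and 4 partly by how extensive the elevation is. That is a crude signal and not a measure of area.

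Nor does the argument carry over fully to days without topical treatment. That diary item asks yes or no for each day, whatever the area treated (Protocol 11.3.4.3), so area acts on it only indirectly.

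Finally, adjusting for the three randomisation factors is a conventional choice, and baseline EASI and SCORAD are tabulated by arm (Protocol 14.3.3), so a large imbalance would be visible. That limits the importance of the point. It does not give a reason to leave the covariate out.

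**Conclusion.** The point holds as a modest one about efficiency. The TCS-amount model and its log-scale version omit a continuous baseline measure that is already collected and plausibly prognostic. The size is unknown: from a 0.2% loss in SE if the covariate is useless, through 1.8 to 4.4% gained at a partial r of 0.2 to 0.3, to 13.2% at 0.5. This rests on the assumed r, on a single-period approximation with no dropout, and on grams being roughly linear in BSA.

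A reader might take the omission as a source of bias. It is not: leaving missing data aside, randomisation keeps the current comparison valid, and its confidence interval already allows for chance imbalance. Both outcomes are 'Other' endpoints (Panel 4) outside the hierarchy of primary and secondary endpoints (Protocol 14.3.6), so neither the sample size nor any confirmatory conclusion is affected.

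**What to change.** Before unblinding, add baseline BSA (SCORAD component A) as one continuous covariate, as a main effect, to the TCS-amount model of Protocol 14.3.10 and to the log-scale model in SAP 6.6.5. Apply it under both assumptions about unreturned tubes. Name this one covariate, so that no choice between BSA and EASI remains once the data are seen. A by-visit interaction is optional; it lets the slope fade over time but uses 13 slopes instead of one. For days without topical treatment the covariate is optional. If the sponsor prefers to keep the current model as the main one, the adjusted model can be a named sensitivity analysis beside those the SAP already adds.

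The cost is one model term, about one degree of freedom and a sentence in the SAP. No new data are needed.
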